## DOES XYREM® INFLUENCE BRAIN DOPAMINE IN PATIENTS WITH NARCOLEPSY?

## A PET IMAGING INVESTIGATION

PROTOCOL: 017/2014, V5.0

filename: CAMHPET-CTA-A-98-01\_StudyProtocol\_V6\_20170913.docx

PI: [name]  
QI: [name]  
REV: SEPTEMBER 13TH, 2017

Protocol Version	Date Issued	Summary of Revisions
V 1.0	24-Feb-2014	- original REB submission
V 2.0	08-Apr-2014	
 
- removal of stimulant using group and all related text (including associated consent form)
 
- removal of antidepressants as an exclusion
 
- revision of negative drug test requirement on scan days
 
- expansion of precautions after taking Xyrem®
 
- minor corrections as necessary
 

V 3.0	09-Dec-2014	
 
- change in title
 

V 4.0	22-Jun-2015	
 
- change to [name] clinic location/contact information
 
- change to study start/finish dates
 
- addition of Data Management and Regulatory Issues sections
 
- corrections and reformatting as necessary
 

V 5.0	05-Jun-2017	
 
- addition of [name] as Co-Investigator, [name] as monitor
 
- addition of healthy control group
 
- request for permission to access participants' GP and/or medical records for medical screening (optional)
 
- additional blood sample taken at 0.5 hours post Xyrem®
 
- corrections and reformatting as necessary
 

V 6.0	13-Sep-2017	
 
- removal of [name] and TWH-UHN as a study Co-investigator / site with subsequent changes to: Site Number; Recruitment and Screening procedures
 
- slight modification to inclusion criteria indicating that all narcolepsy participants will have a confirmed diagnosis, as determined by a sleep specialist
 

## 2. BACKGROUND AND RATIONALE

**Animal data suggest that the sedative drug Xyrem® (Sodium Oxybate, Gamma-hydroxybutyrate (GHB)), used in treatment of patients with narcolepsy, might act on the brain dopamine system, but human findings are lacking.**

GHB is a short chain endogenous fatty acid and GABA metabolite that has sleep-inducing CNS depressant effects. Sodium oxybate, the sodium salt of GHB is approved in Canada (as "Xyrem®") for the (night-time) treatment of cataplexy in patients diagnosed as having narcolepsy with cataplexy (hereafter referred to as "narcolepsy"), a sleep disorder characterized in part by excessive daytime sleepiness. GHB has also been proposed for use as a "neuroprotective" agent in brain disorders such as Alzheimer's disease and major depressive illness, and is also an illicit recreational, abused drug (for reviews see [1] and [2]).

Because Xyrem® is presently approved for clinical use in Canada, and is likely to be used in future for other conditions (e.g., see ongoing clinical trials in "clinicaltrials.gov"), information on the mechanism of action of Xyrem® in subjects having medical conditions which might benefit from its use, might help in understanding the actions and unwanted side effects of this clinically used drug. At present, information on the possible mechanism of action of this drug is limited to animal studies of uncertain relevance to the human and to our preliminary findings in normal subjects.

As described below, the **overall aim** of this investigation is to establish whether an action of Xyrem® on the brain dopamine system in patients with narcolepsy, and in a comparison control group, might explain part of the anti-narcoleptic effect of the drug.

Xyrem®, taken at night, is thought to act by providing continuous "refreshing" sleep to patients with narcolepsy resulting in less periods of daytime sleepiness. The mechanisms of this action are unknown; however, the manufacturer suggests that, based on animal literature, a key action might be a reduction in brain dopaminergic activity during sedation ([3] ; see also below). In this regard, some animal data suggest that an acute dose of Xyrem® depresses activity of brain dopamine neurones and, as a result, dopamine is not released from the nerve ending (see below). On the other hand, investigators leading a study of Xyrem® in Parkinson's disease patients who have sleep problems suggest a different mechanism: that Xyrem®-induced improvement of daytime sleepiness might be caused by above-normal release of dopamine (acting as a modest dopamine-delivering stimulant) during drug withdrawal (which would occur at daytime), as the dopamine built up in the neurone during sleep/sedation is released during the day [4].

Animal data (since 1966 [5]), which could address the above questions are still contradictory and sparse on the nature of GHB-dopamine interactions [6-10] (e.g., review "Does GHB inhibit or stimulate central DA release?") [11]. Cruz and colleagues, on the basis of some electrophysiological findings speculate that "recreational" doses of GHB could *stimulate* dopamine neurones, but that at "higher" concentrations dopamine release might be inhibited [12]. Missing from experimental animal studies are data convincingly showing effects of GHB "withdrawal" on dopamine (i.e., is withdrawal associated with a potentially beneficial dopaminergic hyperactivity?).

Animal findings, however, can only suggest what might occur in the human and need to be confirmed in the clinically relevant human.

In light of the speculations above, the available animal findings, and our preliminary brain imaging findings in normal subjects described below, we wish to determine in a brain imaging study whether Xyrem® might produce a concentration and time-dependent biphasic change in dopamine activity in

(Xyrem®-naïve) patients with narcolepsy. We will also include a group of control subjects in order to determine whether this proposed mechanism of action of Xyrem® might or might not be dependent on disease state.

### How can brain dopamine be measured in living humans?

Extracellular dopamine levels cannot be directly measured in living human brain and **can only be inferred** by conducting a brain imaging (e.g., positron emission tomography; PET) study in which binding of a short-lived radiolabelled probe to components of the brain that are **competitively acted upon by dopamine** is measured.

The radiolabelled probes that we have selected are C-raclopride and C-dihydrotetrabenazine (C-DTBZ). C-raclopride, has low affinity for the D2 dopamine receptor in the dopamine-rich striatum (caudate, putamen), and its binding can be influenced by changes in the concentration of extracellular dopamine. Thus, in imaging studies, administration of a stimulant drug (e.g., amphetamine) that promotes neuronal release of dopamine, and consequently increased extracellular dopamine levels, will reduce the specific binding of C-raclopride in striatum (see [13] and references therein). C-DTBZ binds to the striatal vesicular monoamine transporter (VMAT2) and is sensitive to changes in vesicular neuronal stores of dopamine. This tracer can be used to establish whether vesicular (intraneuronal) dopamine levels are altered during Xyrem® exposure (see [14, 15]).

Should Xyrem® initially decrease activity of brain dopamine neurones and dopamine release during the sedated state, one would expect increased binding of C-raclopride to the D2 dopamine receptor, localized *outside* the dopamine neurone, because of decreased competition from dopamine at the dopamine receptor. We would expect a decrease in C-DTBZ binding to VMAT2 due to attenuated dopamine release, accelerated dopamine biosynthesis, and resultant increase of dopamine in vesicular stores competing with C-DTBZ for binding at VMAT2.

In contrast, during withdrawal from Xyrem®, a time at which some animal data suggest that dopamine release might be increased (as part of a “rebound” phenomenon) we would expect binding of C-raclopride to be decreased, a result of increased competition from dopamine. As described below, our preliminary data in normal subjects support these predictions.

### Preliminary Study supports possibility that Xyrem® induces biphasic dopamine changes in normal human brain.

As part of a Health Canada-approved study (CTA 139361, CTA-A1 154385, CTA-A2 157188) of the influence of Xyrem® on brain dopamine measures we have obtained pilot PET data suggesting that Xyrem® changes both intra- and extra-neuronal dopamine levels in brain, initially depressing dopaminergic activity during sedation but later causing a slight, and potentially beneficial dopaminergic hyperactivity.

Taken together, the preliminary raclopride and DTBZ findings, provide the first hint that Xyrem® might induce, in the normal human brain, initial buildup of intraneuronal dopamine and decreased release, followed hours later by above-normal dopamine release. We now aim to determine whether either of these changes occurs in brain of patients with narcolepsy, the indication for which Xyrem® is approved, following a single dose of the drug.

### 3. OBJECTIVE AND HYPOTHESES

Our **Trial Objective** is to establish, in Xyrem®-naïve patients with narcolepsy and in matched controls, whether a single dose of Xyrem® causes changes in striatal binding of C-raclopride and C-DTBZ that would suggest decreased activity of brain dopamine neurones during the initial sedation and increased dopaminergic activity during Xyrem® withdrawal.

Our **WORKING MODEL**, based on our preliminary human PET brain data, is that an initial action of Xyrem® is to cause, during sedation (which is very fast onset with Xyrem®), depressed activity of nigrostriatal dopamine neurones and dopamine release together with marked intraneuronal biosynthesis of dopamine. At this early time, intraneuronal concentrations of dopamine (competing with C-DTBZ at VMAT2) will be high whereas extraneuronal levels of dopamine (competing with C-raclopride at the dopamine receptor) will be low because (we predict) Xyrem® causes accelerated synthesis of dopamine while depressing activity of dopamine neurones.

During drug withdrawal, dopamine that has been building up inside the neurone is released, leading to increased extraneuronal dopamine (accompanied by decreased raclopride binding at the dopamine receptor) and a normalization of dopamine levels inside the neurone. The modestly increased dopamine activity might persist somewhat in drug withdrawal and be beneficial to the patient.

Our **HYPOTHESES**, based on our pilot data and employing a five scan approach, are that, relative to baseline, striatal 1) **C-raclopride binding** will be increased one hour post-Xyrem® but decreased at seven hours, suggesting decreased and increased neuronal dopamine release, respectively, at these times; and 2) **C-DTBZ binding** will be decreased at five hours post-Xyrem®, suggestive of increased intraneuronal vesicular dopamine buildup during Xyrem® exposure. We predict that this biphasic change in dopamine will occur in both narcolepsy and in healthy control study groups.

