## 5. STUDY PARTICIPANTS

### 5.1. Sample Size

A maximum of 15 patients diagnosed with narcolepsy, who are not currently being treated with stimulant drugs (e.g. Alertec®, Ritalin®, or Dexedrine®) to manage their narcolepsy, and a maximum of 15 healthy controls, will complete all study procedures.

Monte Carlo simulations [17] (>10,000) were performed using BP estimates and standard deviations derived from our data in normal subjects and assumed mixed models analysis and constant standard deviations, with full maximum likelihood for evaluation and time treated as categorical variable to facilitate pre-planned comparisons of outcome values. Results indicate that a sample of 15 will provide sufficient power (>80%, 0.05 alpha) to detect changes (baseline vs. GHB day scans, within subject comparisons) of the magnitude observed in the small pilot study for both raclopride and DTBZ binding.

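### The control group is meant to show whether the drug effect depends on disease state, but no between-group contrast is planned and 15 per group is not shown to be adequate for it

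*Combined protocol and SAP*

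**What the plan says.** All references are to the combined protocol and SAP.

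- **Section 2 (Background and Rationale)** gives the reason for the controls: "in order to determine whether this proposed mechanism of action of Xyrem® might or might not be dependent on disease state".
- **Section 3 (Objective and Hypotheses)** sets the objective of establishing, "in Xyrem®-naïve patients with narcolepsy and in matched controls, whether a single dose of Xyrem® causes changes in striatal binding" of the two tracers. The hypotheses end: "We predict that this biphasic change in dopamine will occur in both narcolepsy and in healthy control study groups".
- **Section 5.1 (Sample Size)** allows "A maximum of 15 patients diagnosed with narcolepsy" and "a maximum of 15 healthy controls, will complete all study procedures". The only power statement is that "a sample of 15 will provide sufficient power (>80%, 0.05 alpha) to detect changes (baseline vs. GHB day scans, within subject comparisons") of the pilot magnitude. No power, precision or margin is given for patients against controls.
- **Section 13 (Statistical Analysis)** uses a mixed model for raclopride with time as the only named factor, Bonferroni-adjusted pairwise comparisons if time is significant, and a paired t-test for DTBZ. It allows demographic covariates. It names no group factor, group-by-time term or two-sample comparison, and does not say whether the models are fitted by group or on all participants together.

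**The concern.** Whether a drug effect depends on disease state is a question about the difference between two changes. The plan has no analysis that estimates that difference, so the reader would be left comparing within-group results.

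That comparison misleads in both directions. A significant change in one group only does not show that the groups differ. Significant changes in both do not show that they respond alike, since one group could have a much smaller effect and still reach significance. If the groups are analysed together without a group term, the results say nothing about the difference.

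At stake is the conclusion the controls were added to support. The report could state that the mechanism is, or is not, shared by patients and controls without an estimate of the difference or its uncertainty. The power figure in Section 5.1 could also be taken to cover a comparison it was not calculated for.

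**Working it through.** **Inputs from the documents.** At most 15 per group; >80% power at alpha 0.05 for within-subject change (5.1). Pilot raclopride changes in two subjects: +6% and +13% early (mean +9.5%), -7% and -6% at six hours (mean -6.5%). Pilot DTBZ change at six hours: -14% (Section 2).

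**The plan's own figure.** The >80% cannot be reproduced, because neither the SD of change nor the simulation settings are given. I therefore worked backwards from the stated power.

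**Assumptions.** Two-sided alpha 0.05, a paired t-test standing in for the simulated mixed model, equal SD of change in both groups, analysis on percent change, and all 15 per group completing.

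**Step 1: effect implied by the within-group power.** Solve the noncentral-t power of a paired t-test with n = 15 (14 df) for d = effect / SD of change. For 80% power, d = 0.778.

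**Step 2: precision of the group difference.** The 95% CI half-width for patient-minus-control change is t(0.975, 28 df) × SD × √(2/15) = 2.048 × 0.365 × SD = 0.748 SD. Relative to the effect it is 0.748 / d.

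**Step 3: what a comparison could detect.** Two-sample noncentral-t power, 15 against 15, for a true difference equal to the whole effect (absent in one group) or half of it.

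**Step 4: how often both groups are significant when one has half the effect.** Multiply the two within-group powers. At the 80% point: 0.80 × 0.29 = 0.23.

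| Within-group power | d | Half-width / effect | Power, effect absent in one group | Power, effect halved in one group | Both significant, effect halved in one group |
|---|---|---|---|---|---|
| 80% | 0.778 | 96% | 54% | 18% | 23% |
| 90% | 0.901 | 83% | 66% | 22% | 33% |
| 95% | 1.002 | 75% | 75% | 26% | 42% |
| 99% | 1.193 | 63% | 88% | 35% | 57% |

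**In percentage points, at exactly 80% within-group power:**

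| Contrast | SD = effect / 0.778 | Half-width = 0.748 × SD |
|---|---|---|
| Raclopride late, -6.5% | 8.4 | 6.2 |
| Raclopride early, +9.5% | 12.2 | 9.1 |
| DTBZ, -14% | 18.0 | 13.5 |

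Each row takes 80% power for its own contrast; the rows do not share one SD.

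**Effect of the Bonferroni step.** If the 80% refers to alpha 0.025 (two comparisons), d = 0.876 and the ratio is 0.748 / 0.876 = 85%.

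**Smaller SDs, for the -6.5% change:**

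| SD of change (points) | Within-group power | Half-width (points) | Half-width / 6.5 |
|---|---|---|---|
| 3 | >99% | 2.2 | 35% |
| 5 | >99% | 3.7 | 58% |
| 6 | 97% | 4.5 | 69% |
| 8 | 83% | 6.0 | 92% |

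Every row meets the stated >80%, so that statement does not tell the reader which row applies.

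**The case against.** Four points can be made for the plan.

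**The hypothesis is about each group separately.** Section 3 predicts that the change occurs in both groups, and two within-group tests can address that. This stands. A reader might infer that the plan predicts equal changes, or a null difference that must be proved. The text does not say so: a change could be present in both groups at different sizes without contradicting Section 3. The between-group question comes from Section 2.

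**The unfavourable figures are boundary cases.** This also stands. The >80% is a floor and the SD is not stated. Section 5.1 assumes constant SDs, so 96% cannot describe both raclopride contrasts: at an SD of 8.35 points, which gives 80% power for -6.5%, the +9.5% contrast has 98% within-group power and a half-width of 6.2 / 9.5 = 66% of its effect. The four individual pilot raclopride values give a pooled SD of √((24.5 + 0.5)/2) = 3.5 points, and so a half-width of 2.6 points, or 41% of 6.5. That SD has 2 degrees of freedom and comes from two normal subjects at 4.5 g rather than 3.0 g, so it cannot carry a design claim, but it shows that good precision is possible.

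**No equivalence margin is called for.** A margin such as half the effect has no basis in the documents. This stands, and none is proposed here.

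**This is a small mechanistic imaging study.** It need not be powered for every question. Agreed, but a stated aim still needs an analysis that addresses it and a conclusion limited to what that analysis supports.

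**Conclusion.** The concern holds in this form: the disease-dependence question in Section 2 has no between-group contrast in Section 13 and no precision or power in Section 5.1. Side-by-side within-group results would not answer it.

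Fifteen per group is not shown to be adequate. Across 80% to 99% within-group power, the 95% CI half-width for the group difference is about 96% to 63% of the whole effect, and power to detect complete absence of the effect in one group is 54% to 88%. These figures rest on the assumptions listed in the working and on full completion of a sample that 5.1 gives as a maximum.

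A reader might go further and conclude that sameness cannot be shown at this size. The documents do not support that, because the answer depends on an SD and a margin that they do not give. With an SD near 3 points the interval would be about a third of the late raclopride effect.

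Adding a group term alone would supply the missing estimate but leave its precision unchanged, so the limits on the conclusion also need to be written down.

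**What to change.** Make the control comparison an estimation aim.

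- **Section 3:** state that the between-group aim is to estimate the patient-minus-control difference in change from baseline, with its 95% CI. Keep the prediction of a change in each group as a separate, within-group hypothesis.
- **Section 5.1:** state that the >80% applies to within-subject change and does not cover the group comparison. Give the SD of change used in the simulation and the expected half-width (about 0.75 SD with 15 completers per group).
- **Section 13:** for raclopride, add group and group-by-time to the mixed model and report the difference in change at one and seven hours. For DTBZ, add a two-sample comparison of change at five hours. Report each as patient-minus-control with its 95% CI.
- **Section 13, interpretation:** state that significance in both groups, or a non-significant difference, will not be read as evidence that the mechanism is independent of disease state.

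If the sponsor wants to claim equivalence, it should justify a margin and the CI level in advance.

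The cost is protocol wording and a small amount of analysis, with no added participants or scans. The downside is that the stated aim for the control group becomes less ambitious.

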## 4. TOTAL NUMBER OF SITES AND NUMBER OF CANADIAN SITES

There will be a single Canadian site:

- 1) Centre for Addiction and Mental Health (CAMH), Toronto, ON Canada

## 5. STUDY PARTICIPANTS

### 5.1. Sample Size

A maximum of 15 patients diagnosed with narcolepsy, who are not currently being treated with stimulant drugs (e.g. Alertec®, Ritalin®, or Dexedrine®) to manage their narcolepsy, and a maximum of 15 healthy controls, will complete all study procedures.

Monte Carlo simulations [17] (>10,000) were performed using BP estimates and standard deviations derived from our data in normal subjects and assumed mixed models analysis and constant standard deviations, with full maximum likelihood for evaluation and time treated as categorical variable to facilitate pre-planned comparisons of outcome values. Results indicate that a sample of 15 will provide sufficient power (>80%, 0.05 alpha) to detect changes (baseline vs. GHB day scans, within subject comparisons) of the magnitude observed in the small pilot study for both raclopride and DTBZ binding.

### 5.2. Patient Population

Subjects are Xyrem®-naïve adult males or females aged 19 or over.

### 5.3. Inclusion Criteria

#### General inclusion

- Able to sign and date informed consent
- Willing and able to complete trial as described in protocol
- Age 19 or over, both genders
- Willing to forgo alcohol and any other sedative-hypnotic drug 48 hours prior to and 24 hours after Xyrem® administration

#### Narcolepsy inclusion criteria (in addition to criteria listed above):

- Must fulfill the International Classification of Sleep Disorders classification for a clinical diagnosis of narcolepsy with cataplexy as determined by a physician specializing in sleep disorders.

### 5.4. Exclusion Criteria

#### General exclusion criteria

- Use of any sedative hypnotics, tranquilizers, anticonvulsants, antihistamines (except non-sedating), benzodiazepines, clonidine, or any medications known to modulate dopamine (e.g. dopamine agonists, antagonists, DAT inhibitors, MAO-A/B inhibitors) at start of baseline period
- Have taken any investigational drug within the past 30 days prior to consent interview
- Have sleep apnea, are shift workers, or have any disorder other than narcolepsy that might be considered to be a cause of excessive daytime sleepiness
- History or evidence of current or recent (within one year of consent) substance abuse or dependence (with exception of nicotine) per interview and urine toxicology; This will include especially any subject who is a heavy alcohol drinker or who cannot control their drinking behaviour

- Any clinically significant unstable or uncontrolled medical or psychiatric disease assessed at physical examination or medical history including but not limited to cardiovascular, hepatic, renal, GI, pulmonary, neurological, or other systemic disease that might interfere with participation in study
- Clinically significant abnormal clinical laboratory urinalysis/blood findings or pre-trial EKG results demonstrating clinically significant abnormality
- Clinically significant history of head trauma, past intracranial surgery, or seizure disorder
- Have ever taken Xyrem® / sodium oxybate / GHB at any time
- Subject is on sodium-restricted diet
- Pregnancy or lactation and women of childbearing potential not taking adequate contraceptive measures [menstrual cycle status on scan days will be documented]
- Hypersensitivity or other contraindications to sedatives
- Current, past, or anticipated exposure to radiation exceeding 20mSv in the last 12 months
- Metal implants or paramagnetic objects within the body which may interfere with MRI
- Claustrophobia
- Succinic semialdehyde dehydrogenase deficiency
- Subject has any other problem that in investigators' opinion would preclude participation in trial

